My current curriculum vitae and the curriculum vitae of physicians/licensed practitioners at this institution who will participate as co-investigators/sub-investigators in this study will be provided to the Study Sponsor. These curriculum vitae will include the extent and type of our relevant experience with pertinent dates and locations.

I certify that I have not been involved in an investigation that was terminated for non-compliance at the insistence of the Study Sponsor, the IRB or EC, or other regulatory authorities. I agree to provide the Study Sponsor sufficient, accurate financial disclosure information. I also agree to update financial disclosure information if any relevant changes occur during the investigation and for one year following the completion of the study.

I understand that this study protocol and the trial results are confidential, and I agree not to disclose any such information to any person other than a representative of the Study Sponsor or the relevant competent authorities without the prior written consent of the Study Sponsor.

Accepted by:

Principal Investigator Signature

Date

Principal Investigator Name

Co-/Sub-Investigator Signature

Date

Co-/Sub-Investigator Name

PROTOCOL SYNOPSIS

Company Name:	Ulthera, Inc.
Protocol Number:	ULT-146
Protocol Title:	Non-Inferiority Study of the Safety and Efficacy of Ultherapy® Using Standard versus Simulines Transducers at a Reduced Energy Level for Patient Comfort
Investigational Device:	Ulthera® System
Development Phase:	Pivotal
Study Objective:	The objective of this study is to demonstrate that the safety and efficacy of Simulines transducers at Energy Level 2 [EL2] is not inferior to treatment with Standard transducers at Energy Level 2 [EL2] in order to limit the energy level of both types of transducers to a maximum of EL2 for lift indications. To fulfill this objective we will be using the same treatment depths and regions treated as those used in the pivotal study that supported the submental/ neck clearance, but at EL2 instead of Energy Level 4 [EL4]. Simulines transducers deliver 2 lines of treatment per pulse (push of the button) versus Standard transducers which deliver 1 line of treatment per pulse.
Study Design:	Prospective, randomized, double blinded, multi-site (up to 8 sites), parallel arm, non-inferiority trial
Number of Subjects:	N = Up to 260 randomized and treated subjects; subjects enrolled may be greater than subjects treated. A minimum of 20 subjects and a maximum of 45 subjects will be enrolled at each site.
Study Treatment Groups:	
Enrolled subjects will be randomized to one of two treatment groups. Subjects will be blinded to their assigned treatment group. All randomized subjects will receive a single, dual depth lower face and neck Ultherapy® treatment. Group A will receive treatment of the lower face and neck with Standard transducers at EL2. The number of treatment lines in each region currently requiring an odd number of lines will be rounded up to even numbers for equivalency in lines of treatment between Standard and Simulines treatment groups (e.g. if 15 standard lines are required in a region on the standard map then this will be rounded up to 16 lines to match the 16 lines required on the Simulines map). Group B will receive treatment of the lower face and neck with Simulines transducers at EL2.
 
Subjects randomized to Group A will receive an Ultherapy® treatment to the lower face and neck with a total minimum pulse count of 672 pulses (+5%) at the 4.5mm and 3.0mm depths using Standard transducers. Energy levels for each transducer will be set to EL2:
 
 • DS 4-4.5 at 0.9J with pitch of 1.5mm and 17 TCPs per line • DS 7-3.0 at 0.30J with pitch of 1.1mm and 23 TCPs per line 
Subjects randomized to Group B will receive a comparable treatment with a total minimum pulse count of 336 pulses (+5%) using the Simulines transducers at the 4.5mm and 3.0mm depths. Energy levels for each transducer will be set to EL2:
 
█ [REDACTED]

Subject Population:	Adults between 30 and 70 years of age who meet the inclusion/exclusion criteria.
Inclusion Criteria:	
 1. Male or female, age 30 to 70 years. 2. Subject in good health. 3. BMI of ≤30. 4. Skin laxity in the area(s) to be treated as determined by trained physician assessors. 5. Willingness to avoid excessive or prolonged exposure to sunlight, tanning

	
booths, sun lamps, or UV light sources.
 
 6. Willingness to apply study provided sunscreen (Neocutis Micro-Day Rejuvenating Cream) daily until study exit to help limit sun exposure. 7. Willingness to avoid or periodically stop use of Sunless Tanners (washout period of two weeks prior to each study visit is required). 8. Understands and accepts the obligation not to undergo any other procedures in the areas to be treated through the follow-up period 9. Willingness to avoid non-emergent dental procedures in the 3 weeks prior to/ post treatment. 10. Willingness and ability to comply with protocol requirements, including returning for follow-up visits and abstaining from exclusionary procedures for the duration of the study. 11. Subjects of childbearing potential must have a negative urine pregnancy test result and must not be lactating at the Screening Visit and be willing and able to use an acceptable method of birth control (e.g. barrier methods used with a spermicidal agent, hormonal methods, IUD, surgical sterilization, abstinence) during the study. Women will not be considered of childbearing potential if one of the following conditions is documented on the medical history: 
 a. Postmenopausal for at least 12 months prior to study; b. Without a uterus and/or both ovaries; or c. Bilateral tubal ligation at least six months prior to study enrollment. 12. Absence of physical or psychological conditions unacceptable to the investigator. 13. Willingness to refrain from use of aspirin, Ibuprofen, Naproxen or any other NSAID prior to study treatment and chronic use during the entire post-treatment study period. Washout period, if chronic user, for 4 weeks prior to the study treatment. After study treatment is completed, limited acute NSAID use, i.e., a maximum of 2-3 doses in any 2 week period, is allowed if needed. 14. Willingness and ability to provide written consent for study-required photography and adherence to photography procedures (i.e., removal of jewelry and makeup). 15. Willingness and ability to provide written informed consent and HIPAA authorization prior to performance of any study-related procedure.

Exclusion Criteria:
	
 1. Presence of an active systemic or local skin disease that may affect wound healing. 2. History of Bell’s Palsy. 3. History of chronic or frequently recurring episodic (recurrent episode in past 12 months) autoimmune diseases such as Multiple Sclerosis, Crohn’s Disease, Psoriasis, Myasthenia Gravis, Lambert-Eaton Syndrome that has required immune suppressant therapy (such as biologic drug or corticosteroid treatment). 4. Palpable thyroid lesion, lymphadenopathy, or other pathological changes within the treatment area. 5. History of skin cancer in the areas to be treated, basal cell nevus syndrome, or jaw cysts. 6. Known allergy or sensitivity to Ibuprofen. 7. Severe solar elastosis. 8. BMI > 30. 9. Significant changes in weight (e.g. more than 5 pounds) over the past 6 months or anticipated significant changes in weight or diet over the course of the study.

	
10. Pregnant within the past year.11. Excessive subcutaneous fat in the area(s) to be treated.12. Excessive skin laxity in the area(s) to be treated as determined by trained physician assessors.13. Significant scarring in the area(s) to be treated that would interfere with assessing results.14. Open wounds or lesions in the area(s) to be treated.15. Severe or cystic acne on the area(s) to be treated.16. Active implants (e.g., pacemakers or defibrillators), or metallic implants in the treatment areas (dental implants not included).17. Inability to understand the protocol or to give informed consent.18. Microdermabrasion, or prescription level glycolic acid treatment to the treatment area(s) within two weeks prior to study participation or during the study.19. Marked asymmetry, ptosis, excessive dermatochalasis, deep dermal scarring, or thick sebaceous skin in the area(s) to be treated.20. History of chronic drug or alcohol abuse.21. Concurrent therapy that, in the investigator's opinion, would interfere with the evaluation of the safety or efficacy of the study device.22. Subjects who anticipate the need for surgery or overnight hospitalization during the study.23. Subjects who, in the investigator's opinion, have a history of poor cooperation, noncompliance with medical treatment, or unreliability.24. Concurrent enrollment in any study involving the use of investigational devices or drugs.25. Current smoker or history of smoking in the last five years.26. Current user of any nicotine-containing products, e.g., e-cigarettes, Nicorette gum, nicotine patches, etc.27. History of the following cosmetic treatments in the area(s) to be treated:
a. Any energy based device (RF, MFU, etc.) procedure for skin tightening within the past year;b. Injectable filler of any type within the past:
i. 12 months for Hyaluronic acid fillers (e.g. Restylane)ii. 12 months for Ca Hydroxylapatite fillers (e.g. Radiesse)iii. 24 months for Long Lasting Hyaluronic acid (e.g. Voluma) and Poly-L-Lactic acid fillers (e.g. Sculptra)iv. Ever for permanent fillers (e.g. Silicone, ArteFill)c. Neurotoxins within the past six months (neuromodulators are allowed in the glabella and forehead, not allowed in the temples, crow's fee or anywhere below the lateral canthus);d. Fractional and fully ablative resurfacing laser treatment within the past two years;e. Nonablative, rejuvenative laser or light treatment within the past six months;f. Surgical dermabrasion or deep facial peels within the past two years;g. Facelifts, neck surgery (e.g. thyroid, neck lifts, neck liposuction, etc.) within the past two years;h. Micro needling within the past year;i. Kybella, Coolsculpting, or Mesotherapy within the past two years; orj. Any history of contour threads.28. History (in the prior year) or current use of the following prescription medications:
--	---------------------------------------------------------------------------------------------------------------------------------------------------------------------------------------------------------------------------------------------------------------------------------------------------------------------------------------------------------------------------------------------------------------------------------------------------------------------------------------------------------------------------------------------------------------------------------------------------------------------------------------------------------------------------------------------------------------------------------------------------------------------------------------------------------------------------------------------------------------------------------------------------------------------------------------------------------------------------------------------------------------------------------------------------------------------------------------------------------------------------------------------------------------------------------------------------------------------------------------------------------------------------------------------------------------------------------------------------------------------------------------------------------------------------------------------------------------------------------------------------------------------------------------------------------------------------------------------------------------------------------------------------------------------------------------------------------------------------------------------------------------------------------------------------------------------------------------------------------------------------------------------------------------------------------------------------------------------------------------------------------------------------------------------------------------------------------------------------------------------------------------------------------------------------------------------------------------------------------------------------------------------------------------------------------------------------------------------------------------------------------------------------------------------------------------------------------------------------------------------------------------------------------------------------------------------------------------------------------------------------------------------------------------------------------------------------------------------------------------------------------------------------------------------------------------------------------------------------------------------------------------------------------------------------------------------------------------------------------------------------------------------------------------------------------------------------------------------------------------------------------------------------------------------------------------------------------------------------------------------------------------------------------------------------------------------------------------------------------------------------------------------

	
 a. Accutane or other systemic retinoids within the past six months; b. Initiation of topical retinoids within the past 6 months or throughout the course of the study; c. Antiplatelet agents/Anticoagulants (Coumadin, Heparin, Plavix); d. Systemic steroids including prednisone; e. Dermal regulators of collagen; f. Initiation of bioidentical hormones or HGH within the past 6 months or throughout the course of the study; or g. Psychiatric drugs that in the investigators opinion would impair the subject from understanding the protocol requirements or understanding and signing the informed consent.

Treatment Outline:
	
 1. Screening: 
 a. Screen for general inclusion/exclusion criteria; b. Obtain informed consent; c. Perform screening photography (2D photography; 5 views: Front, Right 45°, Left 45°, Right 90°, and Left 90°) to confirm eligibility; d. Up to 4 weeks ±7days washout period, if required, for chronic NSAID use. 2. Baseline Visit (The screening visit may not be more than 14 days prior to Baseline. Greater than 14 days between screening and baseline visits will require that the subject be re-screened to confirm enrollment eligibility.): 
 a. Confirm eligibility for participation; b. Obtain pregnancy screen (if applicable); and c. Complete baseline evaluations, including demographics, height, weight, BMI, Fitzpatrick Skin Type, and medical history; d. Perform baseline photography: 
 i. Screening 2D photographs (5 views) will be used if of acceptable quality as Baseline photos. ii. Quantificare 3D imaging system will also be used at up to 3 study sites and in up to 135 subjects. The 3D images will only be used for marketing purposes. iii. Capture adverse events (if necessary). 3. Treatment Visit (The baseline visit may not be more than 14 days prior to Treatment. Greater than 14 days between baseline and treatment visits will require that the subject be re-screened to confirm enrollment eligibility.): 
 a. Subject treatment; and b. Obtain post-treatment 2D images (3 views: Front, Right 90°, and Left 90°). 4. Post-treatment telephone contacts: 
 a. 3±1 days - Capture adverse events b. 7±2 days - Capture adverse events 5. Follow-up Visits for efficacy evaluation: 
 a. 90±14 days 
 i. Obtain images (2D photographs, 5 views; 3D photographs with Quantificare imaging system at applicable site(s)); ii. Obtain Global Aesthetic Improvement Scale (CGAIS and SGAIS); iii. Obtain Patient Satisfaction Questionnaire. b. 180± 21 days 
 i. Obtain images (2D photographs, 5 views; 3D photographs with Quantificare imaging system at applicable site(s));

	
 ii. Obtain Global Aesthetic Improvement Scale (CGAIS and SGAIS). c. 365±30 days 
 i. Obtain images (2D photographs, 5 views; 3D photographs with Quantificare imaging system at applicable site(s)); ii. Obtain Global Aesthetic Improvement Scale (CGAIS and SGAIS); and iii. Obtain pregnancy screen (if applicable). iv. Obtain blinding assessments: Clinician and Subject Blinding Questionnaires. 6. Follow-up Visits for safety evaluation: 
 a. Immediately post-treatment 
 i. Assess for adverse events. b. All follow-up visits 
 i. Assess for adverse events.

Primary Endpoint:
	
1. Efficacy will be assessed based on quantitative measurements of neck and submental lift at 90 days post-treatment compared to baseline. Subject response is defined as ≥ 20 mm² reduction in 2D submental area from baseline. (Note: this is the same methodology and success criteria which supported the FDA clearance of the submental/neck lift indication for this device, Attachment A.) Simulines transducers will be considered non-inferior to Standard transducers using a non-inferiority margin of 15% between the two arms of the trial. The study was powered based on the expected response rate of 73% as seen in the pivotal trial supporting the neck/submental lift indication FDA clearance K121700. The observed response rate of the prior pivotal trial (73%) was higher than the minimum response rate required (65%) for success of the supporting trial.


Secondary Endpoints:
	
 1. Subject response as measured by quantitative improvement measurements of submandibular and submental lift at 180 and 365 days post-treatment compared to baseline. 2. Comparison of improvement in overall lifting and tightening of skin as determined by a masked, qualitative assessment of photographs at 90, 180 and 365 days post-treatment compared to baseline. 3. Assessment of mean change from baseline to 90 days post treatment on the validated, Merz Jawline Grading Scale (MJGS) by independent masked evaluators. 4. Quantificare 3D imaging of up to 135 study subjects to assess volumetric changes from baseline compared to 90, 180, and 365 days post-treatment. 5. Patient satisfaction and patient reported improvement at 90 days post-treatment. 6. Comparison of average treatment times using Simulines transducers compared to average treatment times using Standard transducers. 7. Comparison of average pain scores using a validated Numeric Rating Scale to assess subjects' treatment-related comfort level with Simulines transducers versus Standard transducers. 8. Subject Global Aesthetic Improvement Scale (SGAIS) results assessing overall aesthetic improvement at 90, 180 and 365 days post-treatment. 9. Clinician Global Aesthetic Improvement Scale (CGAIS) results assessing overall aesthetic improvement at 90, 180, and 365 days post-treatment.

Other Data Collected:
	
Prior to treatment, the subject's medical history will be reviewed, a urine pregnancy test will be performed (if applicable), and a physical examination will be conducted. At each subsequent visit, the subject will be queried about adverse events and changes in

	concomitant medications, and the treatment area will be visually examined. An additional pregnancy screening test will be performed at the 365-day follow-up visit (if applicable).
Study Duration:	Given five months for recruitment, the anticipated study duration is seventeen months.

STUDY OVERVIEW

Evaluation / Procedure	Screening Visit	Baseline Visit ⁺	Treatment Visit ⁺	Telephone Contact Day 3 ± 1D Day 7 ± 2D	Day 90±14 Follow-up	Day 180±21 Follow-up	Day 365±30 Follow-up
Informed Consent	√						
Eligibility Assessment (Inclusion/Exclusion ¹)		√ ⁴					
Demographics and Medical History		√					
Pregnancy Screening [^]		√					√
Skin Examination ²		√	√				
Treatment of Face and Neck			√				
Collection of Treatment Time			√				
Subject Assessment of Pain ³			√				
2D images; 3D Images (at applicable site(s))	√	√ ⁴	√ ⁵		√	√ ⁶	√ ⁶
Masked Qualitative Assessments					√	√	√
Jawline Scale		√			√		
Patient Satisfaction Questionnaire					√		
Clinician Global Aesthetic Improvement Scale - CGAIS					√	√	√
Subject Global Aesthetic Improvement Scale - SGAIS					√	√	√
Clinician Blinding Questionnaire							√
Subject Blinding Questionnaire							√
Adverse Event Assessment		*	*	*	*	*	*

+Baseline and Treatment Visits may be separate visits or combined into one visit.

*Complete AE Form when necessary

[^] Pregnancy:

- a. If a subject becomes pregnant after the Baseline visit and after study treatment, the subject should continue to be followed.
- b. If a subject becomes pregnant after the Baseline visit but before study treatment, the subject should be exited from the study.

NOTES:

1. Baseline Form
2. Baseline Clinical Observations (Pre-Treatment) or Clinical Safety and Adverse Events (Post-Treatment and at Follow-up Intervals).
3. Subject Pain Assessment Scale using a validated Numeric Rating Scale. Pain scores should be obtained following each region treated and for each transducer used. Record the average pain score for the entire region treated.
4. Baseline assessment and pre-treatment photos should be obtained within 14 days of study treatment. Screening photos may be used as Baseline photos.
5. Post-treatment images taken 30-60 minutes following Ultherapy® treatment for documentation of any immediate post-treatment AEs.
6. Images taken on this visit, but not a primary endpoint for efficacy.

LIST OF ACRONYMS AND DEFINITIONS

Term	Definition
AE	Adverse Event
CGAIS	Clinician Global Aesthetic Improvement Scale
CV	Curriculum Vitae
EC	Ethics Committee
Elastosis	Degeneration of the elastic tissues
ETE	Expected Treatment Effect
FDA	Food and Drug Administration
GAIS	Global Aesthetic Improvement Scale
GCPs	Good Clinical Practices
IFC	Instructions for Use
IRB	Institutional Review Board
MEEI	Massachusetts Eye and Ear Infirmary, Harvard Medical School
MJGS	Merz Jawline Grading Scale
NRS	Numeric Rating Scale for pain assessment
Pitch	The distance between subsequent thermal coagulations points in a line of treatment
PSQ	Patient Satisfaction Questionnaire
Pulse	Energy delivered by one push of the button on the device handpiece
RF	Radiofrequency
Rhytidectomy	Mini-facelift
Serious Adverse Event	An adverse event that results in or contributes to death or is life threatening. See Section 7.4 for more detail.

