4.3 ELIGIBILITY

4.3.1 INCLUSION CRITERIA

Subjects must meet all of the following criteria for study enrollment:

1. Male or female, age 30 to 70 years.
2. Subject in good health.
3. BMI \leq 30.
4. Skin laxity in the area(s) to be treated as determined by trained physician assessors.
5. Willingness to avoid excessive or prolonged exposure to sunlight, tanning booths, sun lamps, or UV light sources.
6. Willingness to apply study provided sunscreen (Neocutis Micro-Day Rejuvenating Cream) daily until study exit to help limit sun exposure.
7. Willingness to avoid or periodically stop use of Sunless Tanners (washout period of two weeks prior to each study visit is required).
8. Understands and accepts the obligation not to undergo any other procedures in the areas to be treated through the follow-up period.
9. Willingness to avoid non-emergent dental procedures in the 3 weeks prior/post treatment.

10. Willingness and ability to comply with protocol requirements, including returning for follow-up visits and abstaining from exclusionary procedures for the duration of the study.
11. Subjects of childbearing potential must have a negative urine pregnancy test result and must not be lactating at the Screening Visit and be willing and able to use an acceptable method of birth control (e.g. barrier methods used with a spermicidal agent, hormonal methods, IUD, surgical sterilization, abstinence) during the study. Women will not be considered of childbearing potential if one of the following conditions is documented on the medical history:
 - a. Postmenopausal for at least 12 months prior to study;
 - b. Without a uterus and/or both ovaries; or
 - c. Bilateral tubal ligation at least six months prior to study enrollment.
12. Absence of physical or psychological conditions unacceptable to the investigator.
13. Willingness to refrain from use of aspirin, Ibuprofen, Naproxen or any other NSAID prior to each study treatment and chronic use during the entire post-treatment study period. Washout period, if chronic user, for 4 weeks prior to the study treatment. After study treatment is completed, limited acute NSAID use, i.e., a maximum of 2-3 doses in any 2 week period, is allowed if needed.
14. Willingness and ability to provide written consent for study-required photography and adherence to photography procedures (i.e., removal of jewelry and makeup).

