4.5 SUBJECT RANDOMIZATION AND TREATMENT GROUP ASSIGNMENT

At the Treatment visit, only qualified study subjects (i.e., signed the IRB-approved consent form and confirmed eligible) will be randomly assigned according to a computer-generated 1:1 randomization to receive Ultherapy® treatment using either the Simulines or Standard transducers.

Randomizations will be stratified by site and will use randomly selected blocks of size 4 and 6 and will be generated by an electronic database in a reproducible fashion and will be provided to the site by electronic data capture the point that randomization occurs.

Enrolled subjects will be randomized to one of two treatment groups. Subjects and the study clinician performing efficacy assessments should remain blinded to the assigned treatment group. All randomized subjects will receive a single, dual depth lower face and neck Ultherapy® treatment. Group A will receive treatment with Standard transducers at EL2. The number of treatment lines in each region currently requiring an odd number of lines will be rounded up to an even number for equivalency between Standard and Simulines (e.g. if 15 lines are required in a region on the Standard transducer treatment map then this will be rounded up to 16 lines to match the 16 lines required on the Simulines map). Group B will receive treatment with Simulines transducers at EL2.

Subjects randomized to Group A will receive an Ultherapy® treatment to the lower face and neck with a total minimum pulse count of 672 pulses (+5%) at the 4.5mm and 3.0mm depths using Standard transducers. Energy levels for each transducer will be set to EL2:

- DS 4-4.5 at 0.9J with pitch of 1.5mm and 17 TCP's per line
- DS 7-3.0 at 0.30J with pitch of 1.1mm and 23 TCP's per line

Subjects randomized to Group B will receive a comparable treatment with a total minimum pulse count of 336 pulses (+5%) using the Simulines transducers at the 4.5mm and 3.0mm. Energy levels for each transducer will be set to EL2:

The assigned treatment group should be documented on the appropriate study-specific data form and study log.

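### The only scheduled pre-treatment pregnancy test can be up to 14 days old at treatment when Baseline and Treatment are separate visits; testing at the Treatment Visit would make it current (low severity)

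*Combined protocol and SAP*

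**What the plan says.** - **When the test is done.** In the Protocol Synopsis, Treatment Outline item 2 (Baseline Visit) lists "Obtain pregnancy screen (if applicable); and". The Study Overview table and Table 3.1-1 both tick pregnancy screening at Baseline and at Day 365 only. Treatment Outline item 3 (Treatment Visit) contains treatment and post-treatment images, with no test.
- **How many tests.** Section 5.2 says that before treatment "a urine pregnancy test will be performed (if applicable), and a physical examination will be conducted", and it counts the Day 365 test as the second. Section 5 lists the test among the steps that come before treatment. Neither section fixes the day.
- **How far apart the visits may be.** "Baseline and Treatment Visits may be separate visits or combined into one visit" (footnote to both tables). If they are separate, "The baseline visit may not be more than 14 days prior to Treatment"; a longer gap requires re-screening.
- **What happens to a pregnancy in between.** Pregnancy note b, under both tables: "If a subject becomes pregnant after the Baseline visit but before study treatment, the subject should be exited from the study".
- **Eligibility.** Inclusion 11 in Section 4.3.1: "Subjects of childbearing potential must have a negative urine pregnancy test result and must not be lactating at the Screening Visit".
- **Randomisation.** Section 4.5 opens "At the Treatment visit, only qualified study subjects" and has those subjects allocated 1:1 at that visit, once confirmed eligible.
- **Pre-medication.** Section 5.1.2 has every subject take ibuprofen 800 mg between one and two hours before treatment. It does not say where the dose is taken.

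**The concern.** Note b shows that the sponsor foresaw a pregnancy arising between Baseline and treatment and decided that such a subject should not be treated. With separate visits, nothing in the schedule looks for one. The rule then acts only if the subject reports a pregnancy or a site tests on its own initiative.

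At stake is subject protection: a pregnant subject could be given ibuprofen, randomised and treated without any departure from the plan. The documents name no pregnancy-specific harm from the device, and required contraception lowers the chance of the event. The stakes are therefore modest, but the change needed is small.

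**Working it through.** The plan gives no figure to reproduce here. The check consists of counting tests and visit windows, followed by an illustration of size.

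**1. Age of the result and number of tests**

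Inputs: test at Baseline (Treatment Outline item 2, both tables); Baseline to Treatment at most 14 days (Treatment Outline item 3); visits may be combined (table footnote); one further test at Day 365 (both tables, Section 5.2).

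| Arrangement | Maximum age of result at treatment | Tests before treatment | Total with Day 365 |
|---|---|---|---|
| Current plan, visits combined | 0 days | 1 | 2 |
| Current plan, visits separate | 14 days | 1 | 2 |
| Test moved to the Treatment Visit | 0 days | 1 | 2 |
| Baseline test kept, repeated when visits are separate | 0 days | 2 | 3 |

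**2. Whether another provision already requires a treatment-day test**

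The pre-treatment test in Section 5.2 and the ordering in Section 5 are both met by the Baseline test. Section 4.5 requires confirmed eligibility but schedules no test at that visit to support it. Note b says what to do with a known pregnancy and promises no test. No provision fills the gap.

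**3. Whether the test can come before randomisation**

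Randomisation takes place at the Treatment Visit (Section 4.5), so a same-day test can precede it. A positive result is then a screen failure under Section 4.4. It does not create a randomised, untreated subject in the intent-to-treat population of Section 6.3.

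**4. Illustration of size, on assumed inputs**

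The documents do not give the share of subjects of childbearing potential, the share with separate visits, the conception rate or the lag before a urine test turns positive. All four are assumed here.

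Let d be the lag from conception to a positive test, with Baseline at day 0. A Baseline test sees conceptions before day −d. A test on day 14 sees conceptions before day 14 − d. The additional window is (14 − d) − (−d) = 14 days, whatever d is, at a constant conception rate.

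- Assumed conception rate on contraception, 1% to 10% per year. Per 14 days: 1 − 0.99^(14/365) = 0.000385, and 1 − 0.90^(14/365) = 0.00403.
- Low end, 20% of childbearing potential and 25% with separate visits: 260 × 0.20 × 0.25 × 0.000385 = 0.005 subjects.
- High end, 60% and 100%: 260 × 0.60 × 1.00 × 0.00403 = 0.63 subjects.

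Both ends put every separate-visit gap at the 14-day maximum, so shorter gaps would give less.

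Only part of this gain concerns conceptions after Baseline, the case in note b. That share is max(0, (14 − d)/14): 50% at d = 7, 29% at d = 10 and 0% at d = 14. The high end for note b is 0.63 × 0.50 = 0.31 subjects, and the low end is 0. The rest of the gain is pregnancies that began before Baseline but were too early to show there.

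**The case against.** **Moving the test delays some detections.** This stands. With separate visits, a subject detectably pregnant at Baseline is stopped there today. With the test moved, she is found only on the treatment day. If ibuprofen were taken before arrival, which Section 5.1.2 does not rule out, she would be dosed before the result was known. The fix therefore has to place ibuprofen on site, after the result. The later detection remains as a cost.

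**The test count stays the same only under a full move.** This also stands. The eligibility assessment is ticked at Baseline. If a negative result is still wanted there, a treatment-day test is an extra one for subjects with separate visits.

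**Other safeguards exist.** Inclusion 11 requires contraception, exclusion 10 bars pregnancy in the preceding year, Section 5.6 requires pregnancies to be reported, and Section 4.3.2 allows enrolment and treatment on one day. These reduce the number at risk and bar a known pregnancy. None detects an unrecognised one on the treatment day.

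**A reader might infer that the result could be 28 days old.** Inclusion 11 can be read as placing the test at Screening, and "The screening visit may not be more than 14 days prior to Baseline", so 14 + 14 = 28 days. The documents do not support this. The reference to the Screening Visit may govern lactation only, and a site would also have to skip the Baseline test that the Treatment Outline and both tables require. A site that follows the schedule has a result at most 14 days old.

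**A reader might also infer that a treatment-day test makes note b fully effective.** It does not, because a conception within the test's lag still goes undetected.

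**Conclusion.** The point holds as a cheap, low-severity improvement. The schedule itself produces a pre-treatment result that can be up to 14 days old when the visits are separate, and note b then has no scheduled test behind it. With combined visits there is no gap.

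The reading of the schedule is firm. The size of the benefit is not: the number affected cannot be computed from the documents. The range of 0.005 to 0.63 subjects rests wholly on assumed inputs and supports no more than an expectation below one subject. Sample size, error rates and the primary analysis do not change.

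**What to change.** Schedule the pre-treatment urine test at the Treatment Visit, for subjects of childbearing potential, with a negative result required before ibuprofen, randomisation and treatment. State in Section 5.1.2 that these subjects take ibuprofen on site after the result. Align inclusion 11 (synopsis and Section 4.3.1), Treatment Outline items 2 and 3, both schedule tables and Sections 5 and 5.2 to that single time. Note b can stay as written.

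Cost: wording changes, and no added test. The on-site ibuprofen rule means a wait of at least 60 minutes between the result and treatment, because Section 5.1.2 sets that minimum interval after the dose. With separate visits, eligibility is provisional at Baseline and an occasional screen failure falls on the treatment day. Combined visits need no change in test timing.

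Alternative: keep the Baseline test and repeat it on the treatment day only when the visits are separate. This preserves the earlier detection and costs one extra urine test for those subjects.
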